7.4.3. Progress reports

To inform the co-investigators about the study and its progress, a meeting will be held before the beginning of the study, then every year. In addition, a monthly progress report, prepared by the data management team at the PHPT CTU, will be provided to all co-investigators, including the Program Scientists during the trial.

7.4.4. Monitoring of the study

The protocol team will conduct a formal review of the study progress 3, 6, and 12 months after the first enrollment and then every year until completion of the study. At each meeting, the progress of the study will be presented by the principal investigator including safety profiles. More meetings may be organized by the principal investigator as necessary.

7.4.5. Analyses

All patient characteristics recorded at baseline will be summarized using frequencies, medians and confidence intervals.

All endpoints will be summarized using appropriate statistical methods.

Details on these analyses will be further provided in the statistical analysis plan before their initiation.

8. Ethical considerations

8.1 Possible risks including preventive or alleviative measures

8.1.1. Potential Risks to Participants

All patients may experience side effects of the treatments used in the study. Although there are no preventive measures for most side effects of the drugs, in particular anemia and depression, the protocol include close follow up of the patients with regular and systematic monitoring of hemoglobin, signs of depression and other likely adverse effects as detailed in Section 7.2.2, to alleviate the consequences of these adverse effects.

The study involves collection and analysis of data from consenting patients receiving antiretroviral treatment, anti HCV treatment approved and recommended by the Thai FDA, and laboratory monitoring including repeated blood draws that may cause pain, swelling, bruising, and phlebitis.

8.1.2. Potential benefits

Patients may benefit from participating in this study. This study cannot guarantee the success of treatment but it can be beneficial to the patient once HCV viral load decreases, reducing the hepatitis risks and complications caused by hepatitis C infection.

8.2. Recruitment and informed consent (see Patient Information Sheet and Informed Consent Form in Appendix 1, 2)

All co-investigators have passed a training curriculum course on Human Subjects Protection. Specific training will be provided to co-investigators, nurses and counselors prior to the implementation of the study. Training will address the specific aspects of the study, the Good Clinical Practice (GCP) requirements, and procedures for protection of human subjects in clinical research.

Consent form

Written informed consent must be obtained from the subject before any screening procedures. The consent form has been drafted in as practical and non-technical language as possible to ensure that it is understandable to all study subjects. The information included in the consent form has been reviewed by members of the PHPT Community Advisory Board. The informed consent describes the purpose of the study, the procedures to be followed, and the risks and benefits of participation. The consent document specifies the subject's freedom to withdraw his/her participation at any time without compromising access to future medical care. Any changes to the consent document will be submitted to the relevant Ethical Committees.

Consent process

All nurses/counselors who will provide counseling have received training for counseling as well as for Protection of Human Subjects in clinical research and Good Clinical Practice (GCP).

At each site, the nurses/counselors will individually discuss with each potential participant the information included in the consent. Consenting subjects will provide written informed consent for their participation in the study after receiving specific information and counseling. A copy of the consent form will be given to the subject.

The consent form will include names and contact details of the site co-investigator and local Ethic Committees. A copy of the consent document will be given to the patient. In addition, study participants may contact personnel from the Clinical Trial Unit 24 hours a day by phone. The original consent forms will be kept in a locked cabinet at the site. If new information relevant to the patient's consent or her willingness to continue participation in the trial becomes available, the participants and potential participants will be informed.

A notation that written informed consent has been obtained will be made on the patient's case report form. A copy of the consent document will made available to the patient.

- **Step 1:** The nurses/counselors explain the study to the potential subject verbally, providing relevant information (purpose, procedures, risks, benefits, alternatives). The potential subject is provided ample opportunity to ask questions.
- **Step 2:** Following this verbal explanation, the potential subject will be provided with a study informed consent form and sufficient time to consider whether or not to participate in the

research. "Sufficient time" can range from minutes to hours or days. The potential subject may discuss their participation with relative, contact the local ethics committee for this study (named in the informed consent form) or the hospital director to ask questions about the study, their rights and study-related injury.

- **Step 3:** After allowing the potential subject time to read the study informed consent form, the nurses/counselors answer any additional questions, propose the subject to consent to participate in the research and sign the consent form.
- **Step 4:** The nurses/counselors will provide the subject with any significant new findings which may modify the subject's willingness to continue participation.

To prevent a possible risk of a conflict of interest and reduce the risk that patients do not enroll in this cohort under undue influence, the consent process will be primarily performed by the nurses/counselors

8.3. Protection against risk

8.3.1 Institutional Review Board

Prior to the initiation of the study, the protocol and patient consent documents will be reviewed and approved by a national ethics committee at the Thai Ministry of Public Health, the Ethics Committee at the Faculty of Associated Medical Sciences, Chiang Mai University, and at each local hospital site. Subsequent modifications will be submitted for approval before implementation.

8.3.2 Expedited Adverse Experience Reporting

Some adverse events are expected, such as anemia and depression. The protocol includes specific evaluations (hemoglobin level, depression scale) to detect such events so adequate action will be taken to correct these effects (see section 7.2.2). Patients will be informed during the counseling process. In some cases, treatment will have to be interrupted. All clinical adverse events and abnormal laboratory values will be recorded and graded. For severe toxicity and serious adverse events, as defined by International conference on harmonization (ICH) GCP ("International conference on harmonization (ICH) Good Clinical Practice (GCP)," 1996) possibly related to drugs, an Expedited Adverse Experience Report (EAE) will be sent to the Ethics Committees, and program scientists, within three business days of awareness. If a subject dies, events prior to and at the time of death will be transcribed from hospital records, and possible cause(s) of death will be investigated. Management of toxicities and dose modifications for patients will be managed with experts' advice.

8.3.3 Confidentiality

Every effort will be made to maintain the confidentiality of the study participants. All site staff receives initial and ongoing training on Human Subjects Protection and confidentiality. To minimize this risk, study participants will not be identified by name on any study documents but will be identified by the provided patient identification number. All evaluation forms, laboratory specimens, reports and other records will be identified only by the patient identification number to maintain subject confidentiality. All records will be kept in a locked file cabinet in the clinical research unit. All computer entry and networking programs will be processed with patient identification number only. Clinical information will not be released without the written permission of the patient except when necessary for monitoring by the PHPT Clinical Trial Unit (CTU) monitoring staff or the Ministry of Public Health.

8.3.4 Biohazard Containment

As the transmission of blood-borne pathogens can occur through contact with contaminated needles, blood, and blood products, appropriate precautions will be used by all personnel in the drawing of blood and shipping and handling of all specimens for this study, as currently recommended by the US Centers for Disease Control. All infectious specimens will be transported using requirements for shipping infectious substances.

8.3.5 Compensation

Compensation, medical care and other services to be provided to the subjects who may be affected by any complication and policy regarding research related Injuries.

Immediate necessary care is available free of charge to mothers and her infant in the case of medical problems related to participation in this study. However, the study is not responsible for treatments unrelated to the study and no financial compensation will be provided (see Patient Information Sheet Appendix 1).

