7.1.2. Inclusion and exclusion criteria

The population enrolled in the study will be HIV infected individuals meeting all screening and inclusion criteria, and none of the exclusion criteria listed in Tables 3 and 4.

Only patients who meet all the following selection criteria can be enrolled in the study.

Table 3: Inclusion Criteria

HCV RNA loads	Have evidence of chronic HCV infection for at least the last 6 months before study entry (at least one detectable HCV viral loads, i.e. ≥ 17 IU/mL, with an antibody test positive at least 6 months before the HCV RNA load).
Liver	Fibrosis Stage F2-3-4 as determined by transient elastography (Fibroscan or other similar equipment). During the first part of the study, priority will be given to patients with Fibrosis Stage F2-3.
Contraception	Negative pregnancy test (on the day of inclusion).

Table 4: Exclusion criteria

Hematology	Anemia (hemoglobin level < 10 g/dL) Platelets $< 50,000$ /mm ³
Liver	Evidence of decompensated liver disease manifested by presence or history of ascites, variceal bleeding, or hepatic encephalopathy or Child-Pugh score greater than A (Participants with documented or suspected hepatic cirrhosis must have either serum alpha-fetoprotein level of 50 ng/ml or less within 24 weeks prior to study entry; or serum alpha-fetoprotein greater than 50 ng/ml but no greater than 400 ng/ml with an imaging procedure that shows no evidence of a hepatic tumor, both obtained within 24 weeks prior to study entry.) Suspicion or evidence of liver cancer. Hepatitis B (this exclusion criteria will be applied only to the first part of the protocol).
Endocrinology	Uncontrolled diabetes. Uncontrolled thyroid dysfunction (thyroid-stimulating hormone, TSH).
Ophthalmology	Retinopathy.
Kidney function	Creatinine clearance < 50 mL/min (Cockcroft).
Immunology	Disease associated with the immune system (such as Crohn's disease, ulcerative colitis, active rheumatoid arthritis, lupus, idiopathic thrombocytopenic purpura, autoimmune hemolytic anemia, cryoglobulinemia with clinical manifestations including leukocytoclastic vasculitis, scleroderma, or severe psoriasis).
Cardiology	Significant heart problems, such as active symptomatic coronary artery disease.

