Neurologic and psychiatric conditions	Have uncontrolled seizures. Have a history of severe mental problems. Uncontrolled depression or other psychiatric disorder, such as untreated Grade 3 psychiatric disorder, Grade 3 disorder not amenable to medical intervention. Both selective serotonin reuptake inhibitors and other classes of antidepressants are allowed. Active drug or alcohol abuse or dependence that, in the opinion of the study investigator, could interfere with adherence to study requirements.

Other exclusion criteria related to the use of ribavirin and peg-interferon
	
Pregnancy or no contraception if participant is a woman. Pregnancy or no contraception in the female partner of a male participant. No use of condoms, sperm donation or participation in any other fertilization procedures if participant is a man. Breastfeeding. Other contra-indications to ribavirin (see Package Insert). Allergy to peg-interferon or ribavirin. Current administration of didanosine, zidovudine or stavudine. Have taken the following drugs within 6 weeks before study entry: rifampin, rifabutin, pyrazinamide, isoniazid, G-CSF (filgrastim), GM-CSF (sargramostim), or ganciclovir.

Others
	
Have taken any of the following drugs within 6 months before study entry: interleukins, interferons, therapeutic HIV vaccine, thalidomide, pentoxifylline, dinitrochlorobenzene (DNCB), thymosin alpha, thymopentininosiplex, polyribonucleoside, ditiocarb sodium, hydroxyurea, systemic corticosteroids, azathioprine, 6-mercaptopurine, cyclosporin A, or any investigational drug. Any conditions that, in the investigator’s judgment, may compromise the follow up.

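### The injury-care clause in section 8.3.5 names beneficiaries who do not match the adults of both sexes whom the trial enrols

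*Combined protocol and SAP*

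**What the plan says.** Section 8.3.5 (Compensation) opens with a heading-like line about "Compensation, medical care and other services to be provided to the subjects who may be affected by any complication". One sentence then makes the commitment: "Immediate necessary care is available free of charge to mothers and her infant", for medical problems that arise from taking part. The section goes on to disclaim treatment unrelated to the study and adds that "no financial compensation will be provided (see Patient Information Sheet Appendix 1").

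The eligibility sections describe a different group. Section 7.1.2 states that "The population enrolled in the study will be HIV infected individuals meeting all screening and inclusion criteria". Table 2 in section 7.1.1 sets a minimum age of 18. Table 4 lists as exclusions "Pregnancy or no contraception if participant is a woman" and "Breastfeeding", and Table 3 requires a negative pregnancy test on the day of inclusion. Table 4 also has criteria that apply only to men, for example "Pregnancy or no contraception in the female partner of a male participant".

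**The concern.** The sentence in section 8.3.5 is an operative participant-protection provision, not background. It is the only commitment to free care for study-related harm in the protocol text available, and it names a mother and her infant in a trial that enrols neither infants nor mother-infant pairs.

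Who is covered matters because free immediate care is the only remedy the section offers. Treatment is planned for up to 48 weeks. Section 8.3.2 expects anemia and depression, section 8.1.1 acknowledges that most side effects cannot be prevented, and section 7.2.2.2 allows that depression may require hospitalization. Section 8.2 invites potential participants to put questions about study-related injury to the local ethics committee or the hospital director. Anyone who answered from section 8.3.5 as written would describe cover for the wrong group.

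**Working it through.** The plan gives no figure to reproduce on this point. The check compares the text of section 8.3.5 with the eligibility criteria; a short calculation then gives a sense of scale.

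**Beneficiaries against population**

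- *Infants.* Table 2 admits adults only, so no infant can be a participant.
- *Men.* Table 4 addresses male participants and their partners, and Table 6 (section 7.2.1.2) schedules pregnancy tests for partners of male participants. Men are therefore enrolled, and they fall outside the wording.
- *Women without children.* They are eligible and also fall outside the wording.
- *Women with children.* They are eligible too. Table 4 excludes current pregnancy and breastfeeding, not having had children, so these women fall within the word for mothers.

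The literal gap is therefore men plus women without children.

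**Scale, on stated assumptions**

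The number of men is n × (1 − f), where n is the number enrolled and f the female share. Section 7.4.2 gives n = 15 for the first part and 60 if the second part is funded. No section gives f for HCV-positive patients with stage F2 to F4 fibrosis, so it must be assumed.

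- *Assumption A: the whole-cohort share in section 4.5, f = 0.74.* 15 × 0.26 = 3.9, about 4 men. 60 × 0.26 = 15.6, about 16 men.
- *Assumption B: the same cohort, weighted by the HCV antibody prevalences in section 4.1* (8.4% in HIV-positive male conscripts, 4.9% in HIV-infected pregnant women). Male share = (0.26 × 8.4) / (0.26 × 8.4 + 0.74 × 4.9) = 2.184 / (2.184 + 3.626) = 0.376. Then 15 × 0.376 = 5.6, about 6 men, and 60 × 0.376 = 22.6, about 23 men.

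Assumption B borrows prevalences from other populations and periods. It serves only to show that the count moves with the assumed sex mix, and the true number could lie outside both results. Women without children would add to it, but the documents give no data from which to count them.

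**The case against.** The strongest reply is that this is a leftover phrase in a section that is plainly about the participants, with the real terms of cover set out in the Patient Information Sheet. Part of that stands.

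- *The opening line refers to the subjects.* This shows the probable intent, and a reader should not infer that the sponsor means to withhold care from men. But the line has no main verb and promises nothing; the only commitment is in the next sentence.
- *Appendix 1 may state the cover correctly.* It may. Consent pages were removed before review, so their absence is no fault of the plan, and nothing can be said about what participants were told. If the sheet is right, section 8.3.5 disagrees with it; if it repeats the phrase, it needs the same correction.
- *Some participants are mothers.* This is correct, and it defeats the tempting reading that none of the trial's participants is covered. It equally rules out saying that few of the women would qualify, because the documents give no data on how many have children.
- *The mention of an infant is not wholly out of place.* Pregnancy is excluded at entry, but Table 6 continues pregnancy testing during treatment and at 6 months afterwards, so the protocol allows for pregnancy on study. Simply replacing the phrase would delete the only mention of cover for an infant. This bears on the correction, not on whether one is needed.
- *The count of men is soft.* This also stands. The figures rest on a borrowed sex mix, and the total of 60 depends on funding. The mismatch does not depend on either.

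**Conclusion.** The point holds as a minor wording defect in a participant-protection clause. The beneficiaries named in section 8.3.5 do not match the enrolled population, and read literally the section gives men and women without children no stated entitlement to free immediate care for study-related problems.

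A reader might go further and infer that participants are in fact unprotected, or that the consent documents are wrong. The documents support neither: mothers among the participants are covered by the wording, the section's opening line points to all subjects, and Appendix 1 was not available.

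The size can be indicated only roughly: about 4 men of 15, or about 16 of 60, if the parent cohort's 74% female share carries over. That assumption is untested for the HCV-positive subset. That the wording is wrong is clear from the protocol alone; how much it matters in practice depends on the Patient Information Sheet.

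**What to change.** Reword section 8.3.5 so that free immediate care for study-related problems covers all study participants. In a separate sentence, state whether an infant born of an on-study pregnancy is covered; that is for the sponsor to decide, and the present text does not settle it. Then reconcile section 8.3.5 with the Patient Information Sheet, so that the two name the same beneficiaries.

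The cost is one or two sentences, submitted for ethics approval in the way section 8.3.1 already provides for modifications. If the sheet carries the same phrase, it needs a matching revision. Eligibility, sample size, endpoints and analysis are unaffected.

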Appendix 4: Clinical side effects management:

Side Effect	Recommendations and prescription for the patient
Fever/chills	
 • Injecting interferon at bedtime if fever/chills develop 1-3 hours after the interferon injection • Prescribe acetaminophen about 30-60 minutes before weekly interferon injection • Prescribe acetaminophen 1-2 tablets prior to interferon injection and 4-6 hours later if needed up to a maximum of 2,000 mg/day. Thus, do not exceed 6 tablets/day of 325 mg or 4 tablets/day of 500 mg acetaminophen. • Prescribe ibuprofen or naproxen is possible if no other contraindication • Prescribe physical recommendations as: cool sponge bath, ice pack or cold pack when a fever occurs or extra blankets and clothes when chills occur • Encourage notifying the provider if temperature is above 38.5°C for more than 24-48 hours
Muscle and body aches	
 • Injecting interferon at bedtime if body aches develop 1-3 hours after the interferon injection • Prescribe acetaminophen about 30-60 minutes before weekly interferon injection • Prescribe acetaminophen 1-2 tablets prior to interferon injection and 4-6 hours later if needed up to a maximum of 2,000 mg/day. Thus, do not exceed 6 tablets/day of 325 mg or 4 tablets/day of 500 mg acetaminophen. • Prescribe ibuprofen or naproxen is possible if no other contraindication • Recommend trying low-impact exercise such as walking or low-impact aerobics if possible • Recommend maintaining adequate fluid intake (at least six to eight non-caffeinated glasses/day) • Recommend applying warm moist heat or massaging areas
Headaches	
 • Recommend maintaining adequate fluid intake • Prescribe acetaminophen or ibuprofen is possible if no other contraindication • Recommend keeping lights dim, wearing sunglasses or staying in darkened rooms • Recommend getting plenty of rest
Fatigue	
 • Recommend trying low-impact exercise such as walking or low-impact aerobics if possible • Recommend maintaining adequate fluid intake (a caffeinated beverage in the morning is acceptable) • Recommend taking a short nap during the day • Recommend lessening your work schedule if possible • Recommend eating well-balanced meals every day
Depression	
 • If mild depression symptoms (according to the Beck scale): 
 ○ Encourage patients to talk about their symptoms and to take medications that might help (if indicated) ○ Encourage discussion about thoughts of harming him/herself or someone else ○ Encouraging patients to go to the nearest emergency room if feeling in danger of harming him/herself or others ○ Advising to do mild to moderate exercises at least 3 times/week as directed by your provider ○ Increase monitoring frequency of depression evaluation ○ Prescribe antidepressant if necessary and seek for specialized advice • If moderate to severe depression symptoms (according to the Beck scale): 
 ○ Evaluate for suicidal ideation and seek specialized advice ○ Decrease the dose of peg-interferon from 1.5 to 1.0 mcg/kg or less

Side Effect	Recommendations and prescription for the patient
	
 ○ If, severe depressive symptoms or suicidal ideation: discontinue HCV treatment
Anxiety and irritability	
 • Recommend talking to healthcare personnel about symptoms and medications that might help • Recommend always discussing with healthcare personnel thoughts of harming him/herself or someone else • Recommend going to the nearest emergency room if in danger of harming him/herself or others • Recommend doing mild to moderate exercises at least 3 times/week if possible • Recommend trying relaxation techniques such as deep breathing, taped exercises, yoga, Tai Chi or meditation • Recommend avoiding stimulants like caffeine and maintaining adequate fluid intake
Insomnia	
 • Recommend going to sleep and waking up at the same time every day • Recommend to not read or watch TV in bed • Recommend limiting daytime naps • If experiencing anxiousness after ribavirin intake, recommend taking at 4-5 pm instead of before bedtime • Recommend limiting fluid intake for 2 hours before bedtime to avoid having to get up to go to the bathroom • Recommend avoiding caffeinated products, especially in the afternoon and at night • Recommend avoiding heavy meals close to bedtime • Recommend taking warm baths, reading or listening to music, getting a massage • Recommend trying a glass of warm milk (contains tryptophan, a natural sleep agent) • Prescribe diphenhydramine or other medications if indicated
Dry mouth or mouth ulcers	
 • Recommend 
 ○ brushing teeth frequently, especially after eating ○ Avoiding mouthwash containing alcohol ○ Drinking plenty of water or use ice chips or sugar-free lemon drops • Other medications may be needed for mouth sores/ulcers
Bad taste in mouth	
Recommend:
 
 • Using sugar-free lemon drops or real lemon wedges • Eating a small amount of yogurt, 1/2 hour before meals • Drinking lemonade or cranberry juice (monitor glucose levels if diabetes) • Eating food cold or at room temperature • Brushing teeth frequently, especially after eating, to eliminate metallic taste • Using plastic utensils if experiencing metallic taste
Poor appetite	
 • Eating smaller, more frequent (4-6) meals throughout the day • Drinking protein drinks (Carnation Instant Breakfast*, Ensure* or Boost*) • Eating snacks with protein (cheese, peanut butter, eggs) • Eating whatever is appealing even without hunger. Eating a variety of foods • Walking before a meal
Nausea and vomiting	
 • Taking ribavirin with food • Eating small meals • Avoiding foods or smells that trigger nausea • Eating healthy foods. Avoiding greasy, spicy, acidic or sweet foods • Eating ginger in ginger tea, ginger ale or gingersnaps • Eating some crackers or dry white toast if feeling sick in the morning • Prescribe antacids or other medications may be helpful
Diarrhea	
 • Eating more soluble fiber like Bananas, white Rice, Applesauce and white Toast (the "BRAT" diet) • Avoiding foods that are spicy or acidic (like citrus)

Side Effect	Recommendations and prescription for the patient
	
 • Avoiding dairy products up to several days after diarrhea resolves • Maintaining adequate fluid intake (at least six to eight glasses/day) • Prescribe loperamide, methylcellulose or psyllium if needed
Dehydration	
 • Increasing intake of water or non-caffeinated beverages • Avoiding caffeinated beverages
Cough	
 • Increasing intake of water or non-caffeinated beverages • Trying sugar-free hard candy or cough drops
Dry skin/ rashes	
 • Avoiding long, hot showers or baths • Using moisturizing soaps • Using moisturizing lotion after showers • Using mild unscented laundry detergents and avoiding fabric softeners • Using sunscreen • Trying rubbing or pressing on the itchy areas rather than scratching • Prescribe petroleum jelly or other agents on dry, itchy areas
Hair thinning or hair loss	
 • Avoiding harsh hair products such as dyes, perms, gels, sprays and mousses • Using a mild shampoo such as baby shampoo • Avoiding braiding hair; using a wide-tooth comb or soft brush • Wearing a cap, scarf, turban or wig
Injection site reactions	
 • Before injecting, warming the medicine by gently rolling the syringe in the hands for a minute • Rotating/alternating the injection site - thigh, upper arm and abdomen. If thin, using the thigh area might help • Not doing injection into an area that is irritated, bruised or red • Not doing rub injection site • Applying a cold pack • Hydrocortisone cream or other medications can be prescribe to help

Modification of treatment in case of laboratory abnormality:

Peg-interferon alfa-2b must be stopped if: Laboratory exam	Value	Yes	Dose modification
Hemoglobin	< 8.5 g/dL		→ STOP Peg-interferon in case of any of these events
Hemoglobin if history of stable cardiac disease * 4 weeks of a dose reduction	< 12 g/dL*		
WBC	< 1000/mm ³		
Neutrophils	< 500/mm ³		
Platelets	< 25000/mm ³		

Laboratory exam	Value	Yes	Dose modification
Hemoglobin if history of stable cardiac disease	≥ 2 g/dL decrease since the last visit		→ Reduce dose of Peg-interferon of 0.5 mcg/kg If one of these events is verified
WBC	< 1500/mm ³		
Neutrophils	< 750/mm ³		
Platelets	< 50000/mm ³		

Ribavirin dose reduction

Laboratory exam	Value	Yes	Dose modification
Hemoglobin	< 10 g/dL		→ Reduce dose of Ribavirin If one of these events is verified
Hemoglobin if history of stable cardiac disease	≥ 2 g/dL decrease since last visit		

Dose reduction:

If previous dose = 400 mg morning/200 mg evening → **STOP Ribavirin and contact** ☎

If previous dose = 400 mg morning/400 mg evening → Decrease to 400 mg morning/200 mg evening

If previous dose = 600 mg morning/400 mg evening → Decrease to 400 mg morning/400 mg evening

If previous dose = 600 mg morning/600 mg evening → Decrease to 600 mg morning/400 mg evening

If previous dose = 600 mg morning/800 mg evening → Decrease to 600 mg morning/400 mg evening

☎: If Ribavirin dose has already been reduced two times but the listed laboratory abnormalities persist, please contact: [name], [name]

